9.2.2 Sensitivity Analyses

The following sensitivity analyses will be conducted to assess the robustness of the primary analysis:

- As-treated analysis based on actually received treatment
- Analysis on the mITT analysis set
- Analysis on the PP analysis set
- Analysis using the last observed Clinical and Endoscopic Response Score
- Fisher-exact test combined with Cornfield’s exact 95% CI (Cornfield, 1956)(7)

The same analysis conducted for the primary analysis will be repeated for these sensitivity analyses.

Since the definition of remission was modified during the study, an analysis based on the original definition, i.e., rectal bleeding and stool frequency scores of 0 with an endoscopic score of 0 or 1 in the Clinical and Endoscopic Response Score, will also be conducted for reporting purpose.

In addition, sensitivity analyses using multiple imputation (MI) methods and pattern mixture models (PMMs) under missing at random (MAR) and missing not at random (MNAR) assumptions, respectively, will be conducted.

Under the MAR assumption, the missing stool frequency and rectal bleeding scores (Clinical Response scores) for Weeks 2, 4, and 8 will be imputed sequentially by regression-based imputation models using treatment group, baseline characteristics, and outcomes from preceding visits as the predictors. Once the missing Week 8 Clinical Response scores have been imputed, Week 8 Endoscopic Response score will be imputed by regression-based imputation models using treatment group, baseline characteristics, and Week 8 Clinical Response scores as the predictors. Based on the imputed Clinical and Endoscopic Response scores, the remission status at Week 8 will be determined. This imputation procedure will be repeated 100 times, and the primary analysis method will be applied to each of the imputed dataset. A combined estimate of the odds ratio for the treatment group compared to the control group and its 95% confidence interval will be obtained by the methods described in Rubin (1987)(8).

Under the MNAR assumption, a similar MI method described above will be applied. However, in this analysis, only the data from the control group will be used for the regression-based imputation for Clinical Response scores at each visit and Endoscopic Response score at Week 8 by assuming that subjects from the treatment group will follow the same profile as the subjects on the control group after withdrawal from the study (Little & Yau, 1996(9); Ratitch & O’Kelly, 2011(10)).

The primary endpoint will also be analyzed for the following subgroups for the ITT analysis set. The homogeneity of odds ratios across the strata will be tested by the Breslow-Day test at a 0.05 significance level, and the odds ratios for each subgroup will be presented in forest plots.

- Baseline demographic characteristics (age, gender, and race)
- Baseline disease characteristics (previous 5-ASA treatment (yes/no), extent of UC, and severity of UC)
- Geographical region (North America including US and Canada or rest of the world)

The treatment group comparisons after controlling each factor listed above will be conducted by the Mantel-Haenszel test as sensitivity analyses.

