### **3.2 Planned Number of Trial Sites and Subjects**

This trial will be conducted at approximately 110 sites in North America and Europe. Approximately 220 subjects with active, mild to moderate UC will be randomized to receive mesalamine 4 g extended release granules (sachet) or matching placebo in a 1:1 ratio (110/treatment regimen).

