3.2 Determination of Sample Size

The true remission rates at Week 8 for mesalamine 4 g extended-release granules (sachet) and placebo regimens were assumed as 36% and 18%, respectively, based on Kamm et al. (2007)(3), Lichtenstein et al. (2007)(4), and Marteau et al. (2005)(5). Under these assumptions, a sample size of 110 randomized subjects per group will provide at least 85% power to detect a statistically significant treatment group difference in the remission rate at a two-sided 0.05 significance level using the chi-square test.

4 Subject Disposition

The number of screened subjects will be summarized, and for subjects not randomized, the primary reason for exclusion from randomization will be summarized.

The number and percentage of subjects who are randomized, are treated with IMP, prematurely discontinued, and completed the double-blind period of the trial will be summarized with the reason of premature discontinuations. Similar summaries will be made for subjects who are enrolled to the 8-week open-label period.

The time to discontinuation will be summarized by the Kaplan-Meier estimates, and the treatment group difference will be tested by the log-rank test. In addition, reason-specific discontinuation will be summarized by the cumulative incidence estimates.

5 Protocol Deviations

The following protocol deviations will be identified as major protocol deviations:

- Overall IMP compliance of less than 80% during the double-blind period
- Not taking the randomized IMP
- Taking prohibited medications during the double-blind period

The final definition of major protocol deviations will be determined prior to breaking the blind.

The number and percentage of subjects with protocol deviations will be summarized.

6 Analysis sets

For each analysis set, the number and percentage of subjects excluded from it will be summarized by the reason of the exclusion.

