9.1 General Considerations

All statistical tests will be conducted at a two-sided 0.05 significance level.

Statistical tests for the primary and key secondary endpoints will be conducted using a fixed-sequence procedure according to the pre-specified order to maintain the overall Type I error rate to a two-sided 5%. All other secondary endpoints will be tested without adjustment for multiplicity.

Stool frequency and rectal bleeding scores at each visit will be calculated as an average of the daily scores collected within 5 days prior to the visit (excluding the visit day and the day before the visit day if the bowel preparation is needed on the day before the visit). If the daily scores in this period are available for fewer than 3 days, the average score will be considered missing. The average scores will be rounded to the nearest integer for the final score determination (e.g., 0.3 will be rounded to 0, and 0.5 will be rounded to 1).

The average scores will be calculated at Visit 2 (Week 2), Visit 3 (Week 4), and Visit 4 (Week 8) for the double-blind period, and Visit 6 (Week 10) and Visit 7 (Week 16) for the open-label period. Although both Visit 4 and Visit 5 are designated as Week 8 in the double-blind period, Visit 4 corresponds to the visit for the endoscopic assessment, and therefore, the stool frequency and rectal bleeding scores will be calculated at Visit 4. Similarly, the scores will be calculated at Visit 7 for the end of the open-label period instead of at Visit 8.

However, in one section (Section 7.1.3) of Protocol Amendment 2, it was unintentionally indicated that the scores would be calculated at Visit 5 and Visit 8 instead of Visit 4 and Visit 7. As a result, some of these subjects completed the diary fewer than 3 days within 5 days prior to Visit 4 and/or Visit 7 but completed 3 or more days prior to Visit 5 and/or Visit 8. Therefore, for those subjects who consented with Protocol Amendment 2, the average scores calculated at Visit 5 and/or Visit 8, as indicated in Section 7.1.3 of Protocol Amendment 2, will be used if the average scores at Visit 4 and/or Visit 7 are missing. Handling of other missing data in the statistical analyses will be described for each endpoint.

For the endoscopic assessment, the outcomes determined by the independent central reading procedure will be used for all analyses.

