9.2 Primary Endpoint(s)

9.2.1 Primary Variable(s) Analysis

The primary efficacy analysis will be based on all randomized subjects (ITT analysis set). The proportion of subjects with remission, defined as rectal bleeding score of 0 and stool frequency score of “0” or “1 with at least 1 point decrease from baseline” with an endoscopic score of 0 or 1 in the Clinical and Endoscopic Response Score at Week 8, will be compared between treatment groups using a chi-square test without a continuity correction at a two-sided 0.05 significance level. Subjects who discontinue the double blind regimen before Week 8, as well as subjects with missing remission assessment at Week 8, will be considered not having achieved remission. The odds ratio for the treatment group compared to the control group will be estimated and its 95% confidence interval will be provided using the Woolf’s approximation (Woolf, 1955)(6).

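### The imputation analyses in SAP 9.2.2 ignore an observed Week 8 endoscopy when the Week 8 diary is missing, and the control-based version reaches beyond its stated withdrawal rationale; the effect on the odds ratio is small

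*SAP*

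**What the plan says.** SAP 9.2.1 counts a missing Week 8 remission assessment as non-remission. SAP 9.2.2 then plans two model-based checks on that rule.

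- **MAR version.** Missing stool frequency and rectal bleeding scores at Weeks 2, 4 and 8 are imputed in sequence, "using treatment group, baseline characteristics, and outcomes from preceding visits as the predictors". Endoscopy comes last: "Once the missing Week 8 Clinical Response scores have been imputed, Week 8 Endoscopic Response score will be imputed", with the Week 8 clinical scores among its predictors. The combined result is an odds ratio with a 95% confidence interval.
- **MNAR version.** The same scheme is used, but the imputation models for clinical scores at each visit and for Week 8 endoscopy are fitted to control-arm data only. The stated assumption is that treated subjects "will follow the same profile as the subjects on the control group after withdrawal from the study".

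SAP 9.1 supplies two relevant facts. First, a visit score is missing when fewer than 3 daily scores are available in the 5-day window. Second, the Week 8 diary score belongs to Visit 4, which is also the endoscopy visit. It records that "some of these subjects completed the diary fewer than 3 days within 5 days prior to Visit 4", and it substitutes the Visit 5 average for subjects who consented under Protocol Amendment 2.

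**The concern.** The sequence suits subjects who miss both Week 8 components, or only the endoscopy. It has no step for the reverse pattern, endoscopy observed and diary missing. Week 8 endoscopy is measured at the same visit as the diary score, so it is not an outcome from a preceding visit and is not in the predictor list. For these subjects the model in effect assumes that Week 8 symptoms are unrelated to the endoscopic result once treatment, baseline and earlier visits are known. A missing-at-random analysis should condition on the observed data, and here a highly relevant observed value is left out.

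The control-based version adds a mismatch. Its reason covers what happens after a subject leaves, but the rule covers all missing scores. A mesalamine subject who stayed on drug and missed a few diary evenings is imputed from placebo models for no stated reason.

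At stake is how well the only two analyses that model the missing data can support the rule that missing means failure.

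**Working it through.** **1. The plan's own figure.** SAP 3.2: rates "were assumed as 36% and 18%, respectively", and "a sample size of 110 randomized subjects per group will provide at least 85% power". SAP 9.2.1: the test is run "using a chi-square test without a continuity correction at a two-sided 0.05 significance level". With pooled rate 0.27:

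z = [0.18 − 1.96·√(2·0.27·0.73/110)] / √[(0.36·0.64 + 0.18·0.82)/110] = (0.18 − 0.1173)/0.0586 = 1.07, so power = 0.857.

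The stated power reproduces. The true odds ratio is (0.36/0.64)/(0.18/0.82) = 2.56.

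**2. Who is affected.** Remission needs both components. A subject with observed endoscopy 2 or 3 is not in remission whatever the diary. The omission therefore matters when endoscopy is observed at 0 or 1 and the diary is missing.

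**3. Direction.** Write D for diary remission, E for endoscopy 0 or 1, and H for the earlier-visit history. The true probability averages P(D | H, E) over subjects with E. The SAP sequence averages P(D | H) instead. This is lower whenever D and E are positively associated given H.

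As a rough illustration, at a latent correlation of 0.5 the calibrated marginal rates on mesalamine are 0.48 (D) and 0.58 (E). With no history used, the imputed joint rate would be 0.48 × 0.58 = 0.28 against a true 0.36. Weeks 2 and 4 recover part of the gap, to about 0.31.

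**4. Size among affected subjects.** Assumptions, none of them in the documents:
- latent correlation of Week 8 diary with endoscopy from 0.15 to 0.7;
- Weeks 2 and 4 correlated 0.45 and 0.6 with the Week 8 diary, and 0.3 and 0.4 with endoscopy;
- diary missing completely at random.

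Simulation with 400,000 subjects per arm, calibrated to 36% and 18%, gave these imputed remission rates:

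| Correlation | MAR, mesalamine | MAR, placebo | Control-based, mesalamine |
|---|---|---|---|
| 0.15 | 36.6% | 18.2% | 30.6% |
| 0.24 | 35.0% | 16.9% | 29.0% |
| 0.5 | 30.5% | 13.0% | 24.6% |
| 0.7 | 26.6% | 10.4% | 20.7% |

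Placebo under the control-based version equals placebo under MAR. At 0.3 the MAR values are about 34% and 16%. Adding observed Week 8 endoscopy to the MAR model returns about 36% and 18% throughout. Control-only fitting takes about 6 further points off mesalamine in subjects who never withdrew, and it does so at every correlation, including 0.15.

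**5. Whole-arm rates and odds ratio.** Let s be the affected share, assumed 3% to 15%. Arm rate = (1 − s) × true rate + s × imputed rate. At s = 15% and correlation 0.7:

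- MAR, mesalamine: 0.85 × 36 + 0.15 × 26.6 = 34.6% (down 1.4 points)
- MAR, placebo: 0.85 × 18 + 0.15 × 10.4 = 16.9% (down 1.1 points)
- Control-based, mesalamine: 0.85 × 36 + 0.15 × 20.7 = 33.7% (down 2.3 points)

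Odds ratios from the same formula (MAR; control-based):

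| Correlation | s = 3% | s = 15% |
|---|---|---|
| 0.24 | 2.56; 2.54 | 2.57; 2.48 |
| 0.5 | 2.57; 2.55 | 2.60; 2.50 |
| 0.7 | 2.57; 2.55 | 2.61; 2.51 |

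Under MAR both arms fall together, so the ratio hardly moves. Control-only fitting pulls it slightly towards 1.

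**The case against.** The strongest reply is that the SAP's combined estimate is an odds ratio, and the MAR omission leaves it almost unchanged. That stands. A reader might infer from the lower arm rates that the treatment effect is understated; under MAR it is not.

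Second, the diary gaps that SAP 9.1 reports are in subjects consented under Amendment 2, and many are filled from Visit 5. That also stands. The gap that remains is other subjects with fewer than 3 usable days, and Amendment 2 subjects whose Visit 5 diary is also short. The documents do not say how many there are.

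Third, a control-based analysis is meant to be hard on the active arm, and its wording suggests that withdrawals were intended. This stands in part: a lower mesalamine rate is not in itself an error. But the rule as written has no such limit, and a programmer following it would apply none. A reader might also infer that completers are simply treated as placebo subjects. They are not: observed scores are kept, and imputation still conditions on the subject's own earlier outcomes.

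Fourth, imputation also decides remission for subjects who miss both components, or only endoscopy. For them the planned order loses no observed Week 8 endoscopy. Finally, the last-observed-score analysis in SAP 9.2.2 is another check on the missing-data rule, although it does not model the missing values.

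**Conclusion.** The point holds as a minor specification gap in two sensitivity analyses. An observed Week 8 endoscopy is not used where it is informative, and the control-only rule is wider than its reason.

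The downward direction is conditional. It needs a positive diary-endoscopy association beyond Weeks 2 and 4, which is plausible because both measure the same disease at the same visit, but the documents do not state it. At a correlation of 0.15 the omission causes no understatement. Both the correlation and the 3-15% share are assumptions.

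Within them, whole-arm remission falls by at most about 1.5 points under MAR and about 2 points for mesalamine under the control-based version. The odds ratio stays at 2.56-2.61 (MAR) and, for correlations of 0.3 to 0.7, about 2.48-2.56 (control-based), against 2.56. Nothing here touches the primary non-responder analysis, its alpha or its power.

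**What to change.** Amend SAP 9.2.2 in two places.

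1. Impute the Week 8 clinical and endoscopic scores jointly, for example by fully conditional specification, so that an observed Week 8 endoscopic score predicts missing Week 8 diary scores and the reverse.
2. In the control-based version, limit control-only models to scores after discontinuation of double-blind treatment. For subjects who did not discontinue, impute missing scores under MAR from their own arm.

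It would also help to report, by arm, how many subjects have an observed Week 8 endoscopy and a missing diary after the Visit 5 substitution, since that number determines whether any of this matters. The cost is a few sentences and a changed imputation call. No new data are needed and the primary analysis stays as it is.

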9.3 Secondary Endpoint(s)

9.3.1 Key Secondary Endpoints

The following key secondary endpoints will be analyzed for the ITT analysis set.

1. The proportion of subjects with remission in the primary endpoint and the PGA score of ≤ 1 (Modified Mayo) at Week 8
2. Time to cessation of rectal bleeding, defined as time in days from randomization to the first day of 3 consecutive days with a rectal bleeding score of 0, based on subject daily diary

If the primary efficacy analysis demonstrates a statistically significant difference between the treatment groups, the first key secondary endpoint will be compared using the same statistical method used for the primary efficacy analysis. Only if the analysis for the first key secondary endpoint is statistically significant at a two-sided 0.05 significance level, the second key secondary endpoint will be declared statistically significant when the log-rank test is statistically significant at a two-sided 0.05 significance level. The hazard ratio of cessation of rectal bleeding for mesalamine relative to placebo will be estimated (including the 95% CI) using the Cox proportional hazards model with treatment group as a factor.

For the first key secondary endpoint, subjects who discontinue the double blind regimen before Week 8, as well as subjects with missing assessment at Week 8, will be considered not having achieved the response criteria.

For the second key secondary endpoint, if a subject does not achieve the cessation of rectal bleeding by Day 56, the time to cessation of rectal bleeding will be censored at the earlier of the day that the last diary entry is made or Day 56.

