## 4 SELECTION OF TRIAL POPULATION

### 4.1 Trial Population

#### 4.1.1 Inclusion Criteria

1. Male or nonpregnant female subjects aged 18 to 75 years
2. Newly diagnosed or recurrent mild to moderate UC as defined by Modified Mayo score of  $\geq 4$  but not  $>10$  and a score of  $\geq 2$  for flexible sigmoidoscopy/colonoscopy
3. Extent of colonic involvement as confirmed by flexible sigmoidoscopy; colonoscopy to be performed if flexible sigmoidoscopy cannot establish the upper border of UC involvement, or at the discretion of the Investigator
4. Negative stool test at screening to rule out parasites, bacterial pathogens, and *Clostridium difficile*. Subjects who test positive for *Clostridium difficile* can be rescreened if treated and *Clostridium difficile* negative for 2 consecutive months.
5. Estimated creatinine clearance  $\geq 60$  mL/min
6. Females of childbearing potential must agree to use an adequate contraception during the course of the trial. Accepted forms of contraception are: i.e., implants, injectables, hormonal intrauterine device, combined hormonal contraceptives, sexual abstinence, and vasectomized sexual partner. Sterilized or postmenopausal women may also participate. Women must have a negative serum pregnancy test result at screening and negative urine pregnancy test result at Visit 1 (baseline/randomization)
7. Signed informed consent obtained before any trial-related procedures

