## 4.2 Method of Assigning Subjects to Treatment Groups

At Visit 1/baseline, subjects will be randomly assigned in a 1:1 ratio, to 1 of 2 treatment groups based on a centralized computer-generated randomization schedule via an interactive response technology (IRT). Re-enrollment of subjects is prohibited under any circumstances.

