### **7.1.3 Subject Daily Diary**

The subject daily diary will be completed by the subject every evening starting the day of randomization (Visit 1/Day 1). Subject diary will consist of questions regarding IMP daily intake, stool frequency, and presence of blood content. The score for stool frequency and rectal bleeding will be calculated as an average based on scores collected from 3 day subject recall at Visit 0 or from subject diary data 5 days prior to Visits 2, 3, 4, 6 and 7 (see [Appendix 2](#)). If a subject recorded fewer than 3 days of scores during this 5-day period, the average score will be considered missing.

The subject daily diary and questionnaire will be completed via a validated Interactive Voice Response system (IVRS). Instructions on the use of the subject daily diary and questionnaire will be provided to each trial center.

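### Subjects not bleeding at entry can count as Day 1 cessations in either arm, which dilutes a valid test of the second key secondary endpoint; stratifying the log-rank test by the baseline recall score is a free improvement

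*SAP*

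**What the plan says.** Protocol 4.1.1, criterion 2, admits "Newly diagnosed or recurrent mild to moderate UC as defined by Modified Mayo score of" 4 to 10 with an endoscopic score of at least 2. It sets no floor for the rectal bleeding component. Under Protocol 4.2, "subjects will be randomly assigned in a 1:1 ratio, to 1 of 2 treatment groups"; no stratification factor is named.

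Protocol 7.1.3 states: "The subject daily diary will be completed by the subject every evening starting the day of randomization". The same section defines the baseline bleeding score, which "will be calculated as an average based on scores collected from 3 day subject recall at Visit 0".

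SAP 9.3.1 opens with "The following key secondary endpoints will be analyzed for the ITT analysis set" and defines the event as "time in days from randomization to the first day of 3 consecutive days with a rectal bleeding score of 0". It calls for a log-rank test, with no strata mentioned, and a hazard ratio obtained "using the Cox proportional hazards model with treatment group as a factor". The test is third in a fixed sequence: "Only if the analysis for the first key secondary endpoint is statistically significant at a two-sided 0.05 significance level" can this endpoint be declared significant.

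Elsewhere the SAP does use baseline. The repeated-measures model for change in rectal bleeding score (SAP 9.3.2) includes the baseline value. The subgroup and Mantel-Haenszel analyses in SAP 9.2.2 cover the primary endpoint only.

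**The concern.** The endpoint is meant to show how fast bleeding stops, but its definition does not require any bleeding to stop. A subject without bleeding at entry who records 0 on Days 1 to 3 is an event on Day 1, whatever the treatment. These events fall equally on both arms in expectation. They add variance to the log-rank statistic without adding treatment signal, and they pull the hazard ratio toward 1.

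At stake are power for one confirmatory endpoint and the meaning of its hazard ratio. The primary and first key secondary endpoints are untouched.

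**Working it through.** **1. Can non-bleeders enter?** Modified Mayo is stool frequency + rectal bleeding + endoscopy + PGA (Protocol 7.1.1). With endoscopy 2 or 3, the other items 0 to 3 and a total of 4 to 10, 118 combinations are eligible. Of these, 28 have rectal bleeding 0 (23 of 90 if PGA is at least 1). Example: 1 + 0 + 2 + 1 = 4. These are counts of combinations, not a prevalence.

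**2. The plan's own figure.** The only stated power is at least 85% for the primary endpoint (36% vs 18%, 110 per group, two-sided 0.05; SAP 3.2). With pooled rate 0.27:

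Φ{[0.18√110 − 1.96√(2·0.27·0.73)] / √(0.36·0.64 + 0.18·0.82)} = Φ{(1.888 − 1.231)/0.615} = Φ(1.07) = 85.7%.

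This reproduces. No power or event count is given for time to cessation.

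**3. The mechanism by hand, at an assumed 20% non-bleeders.** Assume 65% vs 45% cessation by Day 56 among bleeders, accurate recall, and 90% of non-bleeders with a Day 1 event.

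- True hazard ratio: ln(0.35)/ln(0.55) = 1.76, log 0.563.
- Bleeders: 88 per arm, 0.65·88 + 0.45·88 = 96.8 events, information about 96.8/4 = 24.2. Expected score: 0.563 × 24.2 = 13.6.
- Log-rank variance on a day with n at risk, D events and share p on mesalamine: V = D·p(1−p)·(n−D)/(n−1).
- Non-bleeders: 0.2 × 220 = 44, with about 40 Day 1 events. Unstratified: V = 40·0.25·180/219 = 8.2. In their own stratum: V = 40·0.25·4/43 = 0.9.
- Unstratified power: Φ(13.6/√32.4 − 1.96) = about 67%. Stratified: Φ(13.6/√25.1 − 1.96) = about 78%.

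This leaves out the four non-bleeders without a Day 1 event, so it runs slightly above the simulation.

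**4. Simulation.** Whole days to Day 56, exponential cessation among bleeders, no dropout, the remaining non-bleeders with an event on Days 2 to 7, 10,000 runs per cell (standard error up to 0.5 point). Power in isolation (%), unstratified → stratified:

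| Baseline score 0 | Accurate recall | Moderate error | Poor recall |
|---|---|---|---|
| 5% | 82 → 85 | 78 → 80 | 75 → 75 |
| 10% | 78 → 83 | 74 → 77 | 72 → 73 |
| 20% | 66 → 76 | 66 → 71 | 68 → 69 |

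Moderate error means that 25% of recall-0 subjects bleed on Day 1 and 5% of the others do not; poor recall means 50% and 10%. If every Day 1 non-bleeder has a Day 1 event, the largest accurate-recall gain rises to 13 points (66.2 → 79.1). The lowest cell overall is −0.2 point, within simulation error. At 2% non-bleeders (3,000 runs): 84.6 → 86.0, 81.3 → 81.8, 75.1 → 74.9.

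A separate run on other assumptions (hazard ratio 1.5, 50% placebo cessation, 10% early diary stop, all non-bleeders with a Day 1 event) gave 54.7 → 58.2, 49.3 → 56.2 and 40.1 → 52.2 at 5, 10 and 20%.

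Type I error in the main setting (20,000 runs): 4.9 to 5.1% unstratified, 4.8 to 5.2% stratified.

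**5. Chance of a formal claim.** All three tests must succeed. Assuming 90% of remitters have PGA ≤1 and a correlation of 0.4 between remission and early cessation, the chance at 20% non-bleeders is 53 → 62 (accurate), 54 → 58 (moderate) and 56 → 57% (poor). At 5% it is 67 → 69, 63 → 65 and 60 → 60%.

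**6. Hazard ratio.** The usual tie approximations (Breslow, Efron) lack the (n−D)/(n−1) factor, so the Day 1 ties carry information of about 40 × 0.25 = 10 with or without strata: exp{13.6/(24.2 + 10)} = 1.49. The simulated medians agree: 1.48 unstratified, 1.48 to 1.49 stratified. Restricting to subjects with baseline bleeding gives 1.76 with accurate recall, 1.67 with moderate error and 1.63 with poor recall.

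**7. Where to cut.** One day of streaks in three gives a recall average of 1/3 = 0.33, which the SAP 9.1 rule would round to 0. That subject was bleeding, yet would sit in the non-bleeder stratum and drop out of the restricted hazard ratio. SAP 9.1 lists only post-baseline visits, so rounding at Visit 0 is open. The simulations did not vary the cut.

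**The case against.** An unstratified log-rank test after unstratified 1:1 randomization is a standard, valid analysis of the endpoint as defined. Stratification is an efficiency choice, for one endpoint tested third. That stands.

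The share of non-bleeders appears nowhere, and at 2% the gain is small or nil. The recall precedes an endoscopy that itself falls 4 to 10 days before randomization, and screening can reach back to Day −21. The score may thus be 4 to 21 days old in a relapsing disease, so accurate recall is the favourable case. Both points stand and set the range above.

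Four stronger readings are tempting, and the documents do not support them:

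- That the result is biased toward mesalamine or Type I error is inflated. Non-bleeders are randomized like everyone else.
- That about a quarter of subjects will be non-bleeders, because 28/118 is 24%. Eligible combinations are not equally common.
- That stratifying contradicts the protocol. Protocol 9.6.3 names the log-rank test and is silent on strata.
- That a stratified Cox model would yield a clean hazard ratio. Step 6 shows it does not.

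**Conclusion.** The point holds as an improvement in efficiency and interpretation, not as an error that invalidates the test. The route to Day 1 events among non-bleeders follows from the documents alone; its size does not.

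Under the assumed 65% vs 45% cessation and 110 per arm, stratifying adds about 3 to 11 power points at 5 to 20% non-bleeders with accurate recall, about 1 to 5 with moderate recall error and about 0 to 2 with poor recall. At 2% non-bleeders it adds about 0 to 2. The chance of a formal claim rises by at most about 9, 4 and 1 points in the three recall cases. No setting showed a material loss. The hazard ratio among subjects with baseline bleeding is closer to the effect on cessation than the ITT figure, but recall error leaves some dilution in it.

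**What to change.** Before unblinding, in SAP 9.3.1:

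- Keep the ITT set and stratify the confirmatory log-rank test by the Visit 0 rectal bleeding recall average, unrounded, 0 versus above 0. The score feeds the eligibility calculation (Protocol 6.2.2), so every randomized subject should have it.
- Next to the ITT hazard ratio, report the hazard ratio among subjects with a baseline average above 0, labelled supportive. Note that stratifying the Cox model does not by itself remove the dilution, and that recall error leaves some in the supportive estimate.
- Record the specification in SAP section 12, which now declares no departure from the protocol analysis.

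Optionally, in SAP 9.3.2, stratify time to normal stool pattern by baseline stool frequency in the same way. That endpoint lies outside the fixed sequence, so nothing confirmatory depends on it.

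The cost is a few sentences and one section 12 entry: no new data, no extra subjects and no randomized subject dropped. Because this is an alpha-controlled test, the timing before unblinding matters; a later switch could look data-driven.
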